### 5.14 Adverse Events

All unsolicited adverse events will be collected from vaccination Day 1 through Day 29 for all subjects and from Day 181 through Day 209 for Placebo crossover subjects. Serious adverse events will be collected for the duration of study participation (i.e. starting at Informed Consent through Day 181 for all subjects, additionally through Day 365 for Placebo crossover subjects, and additionally through Day 730 for Cohort 1 sub-study subjects). In Cohort 2 and 3, events occurring after Day 29 may be assessed initially by telephone contact since these cohorts do not have in clinic visits after Day 29. The details of each event will be recorded on the appropriate CRF and in the source document. The reported events may not represent a verbatim accounting by the subject but should reflect the clinical judgment of the study staff. Refer to [Section 7](#) for additional details about evaluating and reporting AEs.

### 5.15 Prior and Concomitant Medications

Prior and concomitant medications at the screening visit and each subsequently scheduled visit, the details of prior and concomitant medication usage will be collected and recorded on the appropriate eCRF.

Prior and concomitant medications (including non-study vaccines) should be collected from 30 days prior to Day 1 through Day 181 for all subjects, and through Day 365 (6 months after active vaccination) for Placebo crossover subjects, and additionally through Day 730 for Cohort 1 sub-study subjects.

### 5.16 Prohibited Medications

Subject must not have received or be planning to receive any other licensed vaccines or antibiotics or chloroquine from 14 days prior to Day 1 randomization through 11 days after study vaccine administration. For Placebo crossover subjects, the subjects must not have received any other licensed vaccines or antibiotics or chloroquine 14 days prior to Day 181, and the subject must not be planning to receive any other licensed vaccines or antibiotics or chloroquine through 11 days after active vaccination. Subjects must not have received or be planning to receive any other investigational agents throughout the main study up to Day 181 and placebo crossover up to Day 365 (6 months after active vaccination).

### 5.17 Emergency Unblinding

The Investigator may obtain a treatment assignment before Day 181 for a study subject only in the case of medical emergency where knowledge of the treatment is necessary for the management of an adverse event. The Investigator will notify the Sponsor ([Section 7.7.4](#)) immediately after unblinding, document the reason and circumstances for the unblinding event, and distribute unblinding information only as needed for medical management.

### 5.18 Protocol Deviations

The Investigator is responsible for conducting the study in accordance with the protocol. Any deviation from the protocol must be documented in the study file. In addition, deviations must be reported to the IRB as applicable. Subject-specific deviations must be recorded in the subject's source documents and in the subject's protocol deviation eCRF. The Sponsor will review all protocol deviations on an ongoing basis and will be responsible for categorizing protocol

deviations as Important Protocol Deviations (IPDs). IPDs may require additional documentation as requested by the Sponsor.

### **5.19 Completion of Study Participation for Individual Subjects**

An individual subject in VAXCHORA treatment groups of Cohort 1, 2, and 3 is considered to complete study participation after completion of the Day 181( $\pm$ 7) visit and completion of any required safety follow-up. An individual subject in the Placebo crossover groups of Cohort 1, 2, and 3 will be offered VAXCHORA at the Day 181 visit and is considered to complete study participation after completion of the Day 365 (6 months after active vaccination) visit if the placebo crossover subject opts to receive VAXCHORA. The placebo crossover subject who opts not to receive VAXCHORA is considered to complete at Day 181. An individual in the long-term follow-up group of the Cohort 1 sub-study is considered to complete study participation after completion of the Day 730 ( $\pm$ 14) visit and completion of any required safety follow-up.

### **5.20 Early Discontinuation**

An enrolled (randomized) subject is considered to undergo Early Discontinuation if they stop study participation before the study completion visit day of each group.

An enrolled subject may voluntarily withdraw consent for further participation at any time before the day of study completion. The Investigator will request (but cannot require) such subjects to provide the reason(s) for withdrawal of consent and to undergo an Early Discontinuation visit.

In addition, the Investigator, at his or her discretion, may withdraw a subject from further participation in the study. Criteria for withdrawal by the Investigator include:

- Noncompliance with the protocol
- Lost to followup: lost to followup requires documentation of at least 3 unsuccessful attempts to contact subjects. Lost to followup will be determined after subject's projected last visit day.
- Adverse event
- Other reason(s) which, in the opinion of the Investigator, indicates that continued participation in the study is not in the best interest of the subject

### **5.21 Subject Replacement**

Subjects who undergo Early Discontinuation after randomization and before vaccination may be replaced at the Sponsor's discretion. Subjects who undergo Early Discontinuation after vaccination will not be replaced. Neither subject numbers nor randomization numbers will be reused.

### **5.22 Study Completion**

The study is planned to be completed after all subjects have completed the planned visits (or Early Discontinuation), all necessary safety follow-up has been completed, and all data queries are resolved, the eCRFs are signed by the Investigator, and the data are locked. The Sponsor reserves the right to terminate the study prior to the planned study completion.

## 6 STUDY PROCEDURES BY VISIT

The overall summary of evaluations by visit is given in the Schedule of Events in [Appendix A](#). All visits are relative to the day of vaccination, Day 1. Acceptable time windows for the visit schedule are indicated.

### 6.1 Study Visits

#### 6.1.1 Screening Visit (-30 Days to Day 1)

The following will take place during the visit:

- Informed Consent
- Medical History
- Prior and concomitant medications
- Physical Exam
- Vital Signs
- Urine Pregnancy test (females of childbearing potential in Cohorts 1 and 2)
- Inclusion/Exclusion Criteria

#### 6.1.2 Day 1

The Day 1 Visit must occur no more than 30 days after the initial Screening Visit. All eligible, consented/assented, and randomized subjects are vaccinated at this visit.

The following will take place during the visit and *prior to* study vaccine administration:

- Updated Medical History
- Directed Physical Examination, if indicated by updated medical history
- Blood Collection (**pre-dose**) for:
  - Serum Vibriocidal Antibody (SVA)
  - Memory B cells for Cohort 1 only (optional)
- Urine Pregnancy test (females of childbearing potential) Updated prior/concomitant medications
- Vital Signs
- Confirmation Inclusion/Exclusion Criteria are still met
- Randomization

#### **Study Vaccine Administration:**

Subjects will take nothing by mouth (food or water) for 60 minutes before and after consumption of study vaccine.

The following will take place during the visit and *after* consumption of study vaccine:

- In-clinic evaluation of acute side effects at least 30 minutes post-vaccination
- Acceptability/Palatability evaluation
- Adverse event evaluation
- Memory Aid - distribution and training

### 6.1.3 Day 11

The following will take place during the visit:

- Memory Aid-collect and review
- Adverse event evaluation including SAE
- Blood Collection for:
  - Serum Vibriocidal Antibody (SVA)
- Updated concomitant medications

### 6.1.4 Day 29 ( $\pm 2$ )

The following will take place during the visit:

- Adverse event evaluation including SAE
- Updated concomitant medications
- Blood collection for:
  - Serum Vibriocidal Antibody (SVA)

### 6.1.5 Day 91 ( $\pm 7$ ):

#### a) Cohort 1

The following will take place at this visit:

- Serious adverse event evaluation
- Updated concomitant medications
- Blood Collection for:
  - Serum Vibriocidal Antibody (SVA)
  - Memory B cells (optional)

#### b) Cohort 2 and 3

Telephone contact is required to assess the following:

- Serious adverse event evaluation
- Updated concomitant medications

#### **6.1.6 Day 181 ( $\pm$ 7 days): Unblinded**

##### **a) Cohort 1**

The following will take place at this visit prior to unblinding:

- Serious adverse event evaluation
- Updated concomitant medications
- Blood Collection for:
  - Serum Vibriocidal Antibody (SVA)
  - Memory B cells (optional)

The following will take place at this visit after unblinding:

- Consent for sub-study (for the Active Treatment Group only)

##### **b) Cohort 2 and 3**

The following will take place at this visit prior to unblinding:

- Serious adverse event evaluation
- Updated concomitant medications

##### **c) Placebo Crossover Groups only (Cohort 1, 2, 3): optional**

VAXCHORA will be offered to the subjects who were administered Placebo on Day 1 after unblinding.

The following will take place during this visit *prior to* Vaccination:

Subjects will take nothing by mouth (food or water) for 60 minutes before and after vaccination.

- Urine Pregnancy Test for Cohort 1 and 2
- Vital Signs

The following will take place during the visit and *after* vaccination:

- In-clinic evaluation of acute side effects for at least 30 minutes post-vaccination
- Acceptability/Palatability evaluation
- Adverse event evaluation
- Memory Aid - distribution and training

**6.1.7 Day 191 (10 days after active vaccination): for Placebo crossover group only**

The following will take place during the visit:

- Memory Aid - collection and review
- Adverse event evaluation including SAE
- Updated concomitant medications

**6.1.8 Day 209 (±2) (28 days after active vaccination): for Placebo crossover group only**

The following will take place during the visit:

- Adverse event evaluation including SAE
- Updated concomitant medications

**6.1.9 Day 271 (±7) (90 days after active vaccination): for Placebo crossover group only**

Telephone contact is required to assess the following:

- Serious adverse event evaluation
- Updated concomitant medications

**6.1.10 Day 365 (±7) (6 months after active vaccination): for Placebo crossover group only**

Telephone contact is required to assess the following:

- Serious adverse event evaluation
- Updated concomitant medications

**6.1.11 Day 365 (± 14 days) for long term follow-up group (sub-study for Cohort 1 only)**

The following will take place at this visit:

- Serious adverse event evaluation
- Updated concomitant medications
- Blood Collection for:
  - Serum Vibriocidal Antibody (SVA)
  - Memory B cells (optional)

**6.1.12 Day 547 (± 14 days) for long term follow-up group (sub-study for Cohort 1 only)**

The following will take place at this visit:

- Serious Adverse Event evaluation
- Updated concomitant medications
- Blood Collection for:

- Serum Vibriocidal Antibody (SVA)
- Memory B cells (optional)

### **6.1.13 Day 730 ( $\pm$ 14 days) for long term follow-up group (sub-study for Cohort 1 only)**

The following will take place at this visit:

- Serious adverse event evaluation
- Updated concomitant medications
- Blood Collection for:
  - Serum Vibriocidal Antibody (SVA)
  - Memory B cells (optional)

## **6.2 Early Discontinuation Visit**

All subjects who discontinue study participation before the planned study completion Day 181 visit will undergo an Early Discontinuation visit.

If the visit occurs before Day 11, the following will be conducted:

- Review Solicited AEs, unsolicited AEs, and Serious Adverse Events (SAEs)
- Update concomitant medications associated with new or ongoing AEs and any SAEs
- Blood Collection for: Serum Vibriocidal Antibody (SVA)

If the visit occurs after Day 11 and before Day 29, the following will be conducted:

- Review unsolicited AEs, and Serious Adverse Events (SAEs)
- Update concomitant medications associated with new or ongoing AEs and any SAEs
- Blood Collection for: Serum Vibriocidal Antibody (SVA)

If the visit occurs after Day 29, the following will be conducted:

- Review Serious Adverse Events (SAEs)
- Update concomitant medications associated with any SAEs
- Blood Collection for:
  - Serum Vibriocidal Antibody (SVA)
  - Memory B cells (optional): for Cohort 1 only

## **6.3 Unscheduled Visits**

Additional study procedure(s) may be conducted at an unscheduled visit as needed. Examples include repeat specimen collection and additional safety follow-up for an adverse event.

## 7 SAFETY

### 7.1 Definitions

#### 7.1.1 Adverse Event

An Adverse Event (AE) is any untoward medical occurrence in a study participant, regardless of the suspected causal relationship with study vaccine.

The definition of an AE includes:

- A new-onset symptom or disease
- An exacerbation of a pre-existing symptom or disease (worsening in frequency or intensity)
- A new-onset laboratory abnormality considered by the Investigator to be clinically significant
- A new-onset symptom or disease that occurs as a result of a protocol-specified procedure

The definition of an AE does **not** include:

- A pre-existing symptom or disease that does not worsen during the study (even if first disclosed by the subject after the start of the study)
- A medical or surgical intervention such as surgery, endoscopy, tooth extraction, or transfusion (although the condition leading to the procedure or a complication from the procedure may be an AE)
- An uncomplicated pregnancy
- A dosing error without any resulting signs or symptoms
- Any other situation where an untoward medical occurrence has not occurred (e.g. hospitalization for cosmetic elective surgery or social admissions)

The Investigator will attempt to establish a diagnosis based on signs, symptoms, and other clinical information. Whenever possible, the Investigator will report an AE as a diagnosis rather than one or more signs or symptoms. If a clinically significant laboratory abnormality meets the definition of an AE, a diagnosis or clinical signs and symptoms rather than the abnormal laboratory finding should be reported if possible. If no diagnosis is known and clinical signs and symptoms are not present, but the laboratory abnormality is clinically significant by itself, then it should be reported as the AE.

#### 7.1.2 Solicited Adverse Event

A solicited adverse event (solicited AE) is a protocol-specified AE about which the Investigator or designee proactively asks the subjects during a protocol-specified time period. Solicited adverse events for this study are: abdominal pain, nausea, vomiting, diarrhea, headache, lack of appetite, fever, tiredness.

### 7.1.3 Unsolicited Adverse Event

An unsolicited adverse event (unsolicited AE) is an AE that is spontaneously reported by the subject or discovered by the Investigator.

### 7.1.4 Serious Adverse Event

An SAE is an AE (either solicited or unsolicited) which meets any of the following criteria:

- Results in death
- Is life-threatening
- Requires hospitalization or prolongs an existing hospitalization
- Results in a persistent clinically significant disability or incapacity
- Is a congenital anomaly or birth defect
- Requires medical or surgical intervention to prevent one of the above outcomes
- Important medical event

The Investigator will evaluate all AEs for seriousness using the above criteria.

“Life-threatening” means that in the opinion of the Investigator, the subject was at immediate risk of death from the event as it occurred. It does not mean that the event might have caused death had it occurred in a more severe form.

Hospitalization for observation or for elective treatment of a pre-existing condition that did not worsen during the study is not considered an SAE.

Important medical events may be considered serious at the discretion of the Investigator.

These seriousness criteria also apply to the Study Stopping Rules in [Section 7.10](#).

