## 7.2 Severity Grading

The Investigator will grade all adverse events for severity. Adverse events listed in the Toxicity Grading Scale in [Appendix B](#) will be graded according to the criteria in the table. Adverse events not listed in the Toxicity Grading Scale will be graded as follows:

- Mild (Grade 1) – No interference with activity
- Moderate (Grade 2) – Some interference with activity
- Severe (Grade 3) – Significant; prevents daily activity
- Potentially Life-Threatening (Grade 4) – ER visit or hospitalization
- Fatal (Grade 5)

These severity grades also apply to the Study Stopping Rules in [Section 7.10](#).

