**APPENDIX B: TOXICITY GRADING SCALE****Table for Clinical Abnormalities**

VACCINE REACTION	MILD (Grade 1)	MODERATE (Grade 2)	SEVERE (Grade 3)	POTENTIALLY LIFE THREATENING (Grade 4)
Abdominal Pain	Mild, no interference with activity	Some interference with activity	Significant, prevents daily activity	ER visit or hospitalization for hypotensive shock
Anorexia (Lack of appetite)	No interference with activity	Some interference with activity	Significant, prevents daily activity	ER visit or hospitalization
Diarrhea	4 loose stools /24 hours	5 loose stools/24 hours	≥ 6 loose stools/24 hours	ER visit or hospitalization
Fatigue (Tiredness)	Mild, no interference with activity	Some interference with activity	Significant, prevents daily activity	ER visit or hospitalization
Fever	> 100.4 – 101.1°F (≥ 38.0 –38.4°C)	≥101.2 – 102°F (≥ 38.5 –38.9°C)	≥ 102.1°F–104°F (≥ 39°C–40°C)	> 104°F (> 40°C)
Headache	Mild, no interference with activity	Some interference with activity	Significant, prevents daily activity	ER visit or hospitalization
Myalgia	Mild, no interference with activity	Some interference with activity	Significant, prevents daily activity	ER visit or hospitalization
Nausea	Mild, no interference with activity	Some interference with activity	Significant, prevents daily activity	ER visit or hospitalization for hypotensive shock
Vomiting	1–2 episodes/24 hours	> 2 episodes/24 hours	Requires IV hydration	ER visit or hospitalization for hypotensive shock "

When developing this Toxicity Grading Scale, PaxVax referred to the recommendations in the FDA’s Guidance for Industry: Toxicity Grading Scale for Healthy Adult and Adolescent Subjects Enrolled in Preventive Vaccine Clinical Trials ([US FDA 2007](#)).

Diarrhea 1-3 Stools/24 hours: Record as “loose stools” on the AE CRF.

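### Some of the severity and seriousness criteria that feed the stopping rules are inconsistent: fever cut-offs differ by unit, an ER visit is graded differently by recorded term, and the observation-admission exemption is ambiguous

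*Protocol*

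**What the plan says.** Section 7.10 suspends enrollment on one event. Rule 1 is any death or SAE, whatever its cause. Rule 2 is one AE of Grade 3 or higher judged possibly or probably related. Either requires notice to the Medical Monitor within 24 hours. The link to the definitions is made in 7.1.4 and 7.2, each of which says its criteria also apply to the stopping rules; 7.10 does not repeat it.

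**Seriousness.** Section 7.1.4 lists among the SAE criteria "Requires hospitalization or prolongs an existing hospitalization". It then adds "Hospitalization for observation or for elective treatment of a pre-existing condition that did not worsen during the study is not considered an SAE", and also "Important medical events may be considered serious at the discretion of the Investigator". Section 7.1.1 excludes from the AE definition "A pre-existing symptom or disease that does not worsen during the study".

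**Severity.** For AEs not listed in Appendix B, 7.2 gives "Potentially Life-Threatening (Grade 4) – ER visit or hospitalization". Appendix B gives an ER visit or admission as Grade 4, without further condition, for diarrhea, headache, tiredness, anorexia and myalgia. The abdominal pain, nausea and vomiting rows add hypotensive shock after the ER-or-admission wording. Vomiting is Grade 2 above two episodes in 24 hours, and its Grade 3 is "Requires IV hydration". Fever is graded by temperature alone; the Grade 1 cell reads "> 100.4 – 101.1°F (≥ 38.0 –38.4°C".

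**Recorded term.** Section 7.1.1 says "Whenever possible, the Investigator will report an AE as a diagnosis rather than one or more signs or symptoms".

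**The concern.** When one event is enough to suspend enrollment, the classification of that event is the decision. The same reading, visit or admission should therefore get the same grade and seriousness at each of up to 30 sites. Here the result can depend on which temperature unit is read, which term is recorded, or how a sentence is parsed. The grades also feed the 9.4.1 table of solicited AEs of moderate severity or higher, and SAE status feeds the SAE endpoint in 2.2.

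**Working it through.** No sample size, power or alpha figure is involved, and the plan gives no figure to reproduce. The check is a unit conversion and a trace of cases through the two rules.

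**1. Fever row of Appendix B.** Formula: °C = (°F − 32) / 1.8.

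| Reading | Conversion | To one decimal | Grade by °F | Grade by °C |
|---|---|---|---|---|
| 100.4°F | 68.4 / 1.8 = 38.00 | 38.0 | below Grade 1 (strictly greater) | 1 (greater or equal) |
| 101.2°F | 69.2 / 1.8 = 38.44 | 38.4 | 2 | 1 |
| 102.1°F | 70.1 / 1.8 = 38.94 | 38.9 | 3 | 2 |

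In reverse, the °C starting points convert to 38.5 × 1.8 + 32 = 101.3°F (Grade 2) and 39 × 1.8 + 32 = 102.2°F (Grade 3). The printed °F starts are 101.2 and 102.1, so each boundary is 0.1°F apart. The 101.2°F case moves an event into or out of the moderate-or-higher table. The 102.1°F case crosses the rule 2 threshold if the fever is judged related. The protocol names no governing unit.

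**2. ER visit without admission.** Take a related illness with more than two vomiting episodes in 24 hours, an ER visit, no IV hydration, no shock, no admission and no other seriousness criterion. Rule 1 is not met, so rule 2 decides.

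| How the shock qualifier is read | Recorded as vomiting | Recorded as an unlisted diagnosis |
|---|---|---|
| Governs both ER visit and admission | Grade 2, no halt | Grade 4, halt |
| Governs admission only | Grade 4, halt | Grade 4, halt |

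On the first reading the halt depends on the recorded term, and 7.1.1 prefers the diagnosis. If IV hydration is given, vomiting is Grade 3 and rule 2 is met either way. If the child is admitted and the admission counts as an SAE, rule 1 halts whatever the grade.

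**3. Admission for observation only, new AE such as diarrhea (Grade 4 in Appendix B).**

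| How the 7.1.4 exemption is read | SAE by hospitalization? | Related event | Unrelated event |
|---|---|---|---|
| Observation is a separate exclusion | No | Rule 2 halts, 24-hour notice | No halt, unless called an important medical event |
| The pre-existing-condition qualifier governs both phrases | Yes | Rule 1 halts | Rule 1 halts |

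The second reading agrees with 7.1.1: a condition that was already present and did not worsen is not an AE, so it is neither graded nor serious. On the first reading, SAE reporting and tabulation also depend on the investigator's discretion.

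**The case against.** The strongest reply is that items 2 and 3 rest on opposite parsing of the same grammar. If the trailing qualifier is attached to both items throughout, the observation exemption is harmless. If it is attached to the last item only, the ER split between vomiting and a diagnosis disappears. This is fair, and it means that both problems do not arise under one consistent reading. It does not clear the text: the first convention leaves the ER split, the second leaves the exemption, and the fever row is unaffected by either.

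Other points stand and limit the effect:

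- Vomiting on Days 1 to 8 is solicited by name and recorded on its own form (5.13), so the choice of term is narrower than 7.1.1 alone suggests.
- A move between Grade 2 and Grade 4 does not change the moderate-or-higher table.
- The fever mismatch is small.
- The Safety Management Plan and CRF Completion Guidelines are cited but not shown, and may already settle some of this.

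A reader might infer more than the protocol supports:

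- **That Grade 4 without SAE status is a contradiction.** It is not; severity and seriousness are separate scales.
- **That observation admissions would escape 24-hour notice.** A related Grade 4 event still halts enrollment and is notified within 24 hours under 7.10.
- **That some share of SAEs would be lost.** Nothing in the protocol says how many admissions would be for observation, so no such share can be computed.

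**Conclusion.** The point holds as an inconsistency in criteria that decide a halt, not as a general conflict between seriousness and severity. The fever row is wrong on its face at three readings; one of them lies on the rule 2 threshold and one on the moderate-or-higher threshold. The ER split changes a halt only for related events without admission, and only if the shock qualifier covers ER visits. The exemption changes a halt only for unrelated observation admissions, and only if observation is a separate exclusion. For ordinary admissions rule 1 already halts enrollment. How often these cases would occur cannot be estimated from the protocol. The fever grades assume that °C is read to the table's one decimal; unrounded, 38.44 and 38.94 fall between the printed °C bands, which is still not the grade given in °F.

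**What to change.** Reconcile 7.1.4, 7.2 and Appendix B:

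- Name one governing temperature unit and make the other column match its boundaries, including the strict versus non-strict inequality at the Grade 1 start.
- Make the ER and hospitalization wording consistent across the Appendix B rows and 7.2, so that one illness has one grade whether recorded as a symptom or a diagnosis. The sponsor and SMC choose the criterion.
- State in 7.1.4 which reading of the observation exemption applies.

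The cost is a wording amendment to the protocol and the matching CRF guideline. Depending on the choices made, a few more events may be classed as SAEs or as Grade 3 or higher. Each further SAE, and each further Grade 3 or higher event judged related, would pause enrollment for review.
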